5.4.4 Adverse events

Severity of AEs is scaled according to Common Terminology Criteria of Adverse Event (CTCAE version 4.0, [\[R10-4848\]](#)).

Besides analysis with regard to primary system organ class and preferred term, AEs by user-defined AE categories (UDAEC) will be analysed. Definitions of user-defined categories in terms of MEdDRA codes and subsearches can be found in [Section 9.4](#) of this TSAP.

5.4.5 Laboratory parameters

5.4.5.1 General safety laboratory parameters

In this trial the original laboratory values will be converted into standard units and the CTCAE grades will be assigned to all parameters which have a CTCAE definition. For this study, the laboratory parameters and their functional groups, together with the direction of concern are:

Haematology: Haemoglobin (HGB) (-), haematocrit (HCT) (-), red blood cell count (RBC) (-), white blood cells (WBC) (-), platelets (PLT) (-) and reticulocytes (RET) (-),

Differential: Neutrophils (NEUT) (-), lymphocytes (LYMPH) (+ and -), monocytes (MONO) (-), basophils (BAS) (+) and eosinophils (EOS) (+), CD3+ T cell count (CD3V) (-), CD4+ T cell count (CD4V) (-), CD8 T cell count (CD8V) (-), CD56+ natural killer cell count (CD56V) (-), CD 19+ B cell count (+ and -)

Electrolytes: Sodium (NA) (+ and -) and potassium (K) (+ and -)

Enzymes: Aspartate amino transferase (AST) (+), alanine amino transferase (ALT) (+), alkaline phosphatase (ALKP) (+)

Substrates: Total bilirubin (TBILI) (+), glucose (GLU) (+ and -) and creatinine (CRE) (+)

Coagulation: International normalised ratio of prothrombin time (INR) (+), activated partial thromboplastin time (aPTT) (+) and prothrombin time (PRT) (+)

Urine (measured by dipstick): pH, glucose, erythrocytes, leukocytes, protein, nitrite

Biochemistry: Calcium (CA) (+ and -), corrected calcium (+ and -), inorganic phosphate (P) (-), lactate dehydrogenase (LDH) (+), urea (UREA) (+), total protein (TPRO) (-), albumin (ALB) (-), uric acid (URIC) (+), Immunoglobulin A (IGA) (+ and -), Immunoglobulin M (IGM) (-), Immunoglobulin G (IGG) (-), direct antiglobulin test (COOMB), CMV DNA (qual.)

The signs + (-) means the above (below) the reference ranges. For the parameters TPRO, ALB, URIC, IGA, IGM, IGG, and direct antiglobulin test, no CTCAE grade definition is

available. The direction of concern will be investigated with regard to their respective reference ranges.

Urine measurement (based on dipsticks with 0, +, ++, and +++; the more + the worse) will be displayed if available. For urine measurement based on dipsticks conversion rules can be found in [Section 9.3](#).

The grading of hypocalcemia is based on corrected calcium as calcium can be falsely low if hypoalbuminemia is present. The following corrective calculation will be performed:

Corrected calcium (mg/dL) = Total Calcium (mg/dL) – 0.8[Albumin (g/dL)-4)

No correction of the reference range has to be done. The reported reference range of total calcium should be used for analyses.

Corrected calcium can be only derived at a certain time point in case both laboratory values, total calcium and albumin, have been reported for the patient in the same laboratory sample.

The following laboratory parameters are considered as prioritized laboratory values as defined on project level: Haemoglobin, WBC, neutrophils, lymphocytes, platelets, ALT, AST, total bilirubin, LDH, creatinine, uric acid, potassium, inorganic phosphate, calcium, corrected calcium, albumin, CD4+ T cell count. Prioritized laboratory values will be presented in Section 15 of the CTR, while all other laboratory parameters of concern will be displayed in Appendix 16.1.9.2.

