#### 5.2.3.2 Screening for laboratory evidence of tumour lysis syndrome

Tumour lysis syndrome (TLS) is characterized by metabolic derangements caused by the massive and abrupt release of cellular components into the blood after rapid lysis of malignant cells. The release of the intracellular metabolites can overwhelm normal homeostatic mechanisms, potentially leading to hyperuricemia, hyperkalemia, hyperphosphatemia, hypocalcemia, and uremia. This can result in impaired renal function, and in some cases, in acute renal failure and even death ([R10-4517](#)). To allow for early treatment in case TLS develops, vigilant monitoring is recommended. During the first 48 hours after the start of the first infusion of BI 836826 in course 1, and during the first 24 hours after the start of the second infusion in course 1 and of the first infusion in course 2, the below listed laboratory parameters need to be determined to screen for evidence of a tumour lysis syndrome monitored frequently, *i.e.* every 4-8 hours between the time points at which a complete safety laboratory has to be performed. Monitoring for TLS of the second infusion of course 2 and the first and second infusion of course 3 are to be performed while the patient is in hospital. In case of the split first dose administration the same parameters need to be determined during the first 72 hours after the start of the low dose of BI 836826 in course 1, and for other infusions the monitoring should be as above described. The actual date and time of the blood samples should be recorded in the eCRF.

Haematology	haemoglobin, haematocrit, red blood cell count (RBC), white blood cell count (WBC),+ differential, platelets (PLT)
Biochemistry	uric acid, potassium, calcium, inorganic phosphate, lactate dehydrogenase (LDH), creatinine, urea

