5.4.5.2 Tumour lysis syndrome (TLS)/Laboratory signs of cell destruction

The presence of TLS will be mainly investigated via adverse event reporting (see [Section 7.8](#)). In addition, laboratory signs of cell destruction will be investigated based on the laboratory values uric acid, potassium, inorganic phosphate and creatinine. Laboratory signs of cell destruction may be considered present if within the time window of the day of BI 836826 infusion and the following 6 days two or more of these laboratory parameters are considered abnormal simultaneously. Simultaneously means that abnormality of these ≥ 2 lab parameters occurs within 24 hours within the 7 day window after BI 836826 infusion. The definition of abnormal laboratory values is given in [Table 5.4.5.2: 1](#) below. In case laboratory signs of cell destruction are observed, it will be checked whether an AE episode that may indicate clinical TLS is reported within the 7 day time window after BI 836826 infusion. For the respective UDAEC see [Section 7.8](#).

Table 5.4.5.2:1 Definition of abnormal lab values for laboratory signs of cell destruction

Laboratory parameter	abnormal value
Uric acid	$\geq 476 \mu\text{mol/L}$ AND increase from relative baseline by $\geq 25\%$
Potassium	Only if relative baseline is $< 6.0 \text{ mmol/L}$: value $\geq 6.0 \text{ mmol/L}$
Inorganic phosphate	$\geq 1.45 \text{ mmol/L}$ AND increase from relative baseline by $\geq 25\%$
Creatinine	Absolute increase from relative baseline by $26.5 \mu\text{mol/L}$ AND increase from relative baseline by $\geq 50\%$

Definition of relative baseline: relative baseline is the last laboratory value prior to BI 836826 infusion, ie. it will be derived for the four laboratory values separately for each infusion.

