7.8.2 Laboratory data

The analyses of laboratory data will be descriptive in nature and will follow the standard procedure laid down in the DM & SM (Guideline 'Display and Analysis of Laboratory Data' [\(7\)](#)).

Patients will be counted under the initial treatment. The analysis of laboratory data will use the same ‘analysing treatments’ as described for the AEs, except for that the baseline laboratory value (as defined in [Section 6.7](#)) will be included in the ‘on-treatment’ period. Patients having at least one post-baseline laboratory value will be displayed in the descriptive analyses.

Single time courses by initial treatment will be used to display laboratory values over time. The graphs may be truncated if sufficient data is not available. These graphs will be displayed in Chapter 16.1.9.2 of the CTR for the following parameters, using the BI standardized values for haematology and differentials.

Haematology: haemoglobin, WBC count and platelets

Differentials: neutrophils (absolute count), absolute lymphocyte count, absolute Monocyte count and Natural Killer (NK) cells, CD 4 T-cell count

Biochemistry: LDH.

Clinically relevant abnormalities (as defined in [Section 9.2](#)) will also be summarised.

The change of the laboratory value will be calculated for all laboratory parameters from baseline to the end of the treatment for the whole treatment duration. No post-study laboratory values will be considered.

Worst laboratory value and its CTCAE grade (highest CTCAE grade) over all courses will be calculated for each laboratory parameter.

The change of the CTCAE grade of the lab value will be calculated

- from baseline to the last laboratory value on treatment
- from baseline to the worst value on treatment
- from worst value on treatment to last value on treatment

Note: For calculating the change in CTCAE grade from baseline, patients with a CTCAE grade of -9 (no CTCAE grade defined) will be treated as a CTCAE grade 0 for all analyses. In laboratory listings, the CTCAE grade is displayed as -9.

For Uric Acid and Hypokalemia, the CTCAE grade cannot always be assigned by the laboratory parameter itself as two different CTCAE grades have the same laboratory constellation, but are distinguished by additional clinical parameter. In this case a CTCAE grade of -1 will be assigned initially. Patients with a CTCAE grade of -1 will be treated as

- Grade 1 for Uric Acid
- Grade 1 for Hypokalemia

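### SAP 5.4.5.1 looks for phosphate only on the low side, so an isolated rise is not marked as a concern; separately, the SAP contradicts itself on whether uric acid has a CTCAE grade

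*SAP*

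**What the plan says.** **Direction of concern.** SAP 5.4.5.1 gives each laboratory parameter a sign and explains it: "The signs + (-) means the above (below) the reference ranges". The entry "inorganic phosphate (P" is followed by a minus sign alone. The entry "uric acid (URIC" is followed by a plus sign.

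**Tumour lysis in the protocol.** Section 5.2.3.2 describes the release of cell contents as "potentially leading to hyperuricemia, hyperkalemia, hyperphosphatemia, hypocalcemia, and uremia". It requires phosphate and uric acid, among other tests, every 4 to 8 hours around the early infusions.

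**Tumour-lysis analysis in the SAP.** Section 5.4.5.2 uses four markers: uric acid, potassium, inorganic phosphate and creatinine. Table 5.4.5.2:1 calls phosphate abnormal when it is at least 1.45 mmol/L and at least 25% above the last value before the infusion. Laboratory signs of cell destruction are considered present when "two or more of these laboratory parameters are considered abnormal simultaneously", meaning within 24 hours of each other, from the day of infusion through the following 6 days.

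**Grading of uric acid.** Section 5.4.5.1 states: "For the parameters TPRO, ALB, URIC, IGA, IGM, IGG, and direct antiglobulin test, no CTCAE grade definition is" available, and says these parameters are judged against their reference ranges. Section 7.8.2 states: "For Uric Acid and Hypokalemia, the CTCAE grade cannot always be assigned" from the laboratory value alone. It codes such cases -1 and analyses them as Grade 1. For the code -9 the rule in 7.8.2 is: "no CTCAE grade defined) will be treated as a CTCAE grade 0 for all analyses".

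**Prominence.** Section 5.4.5.1 lists both phosphate and uric acid among the prioritised parameters, which go into Section 15 of the report.

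**The concern.** The sign for phosphate in the general list points away from the direction that matters for tumour lysis, a protocol-specified significant adverse event (Protocol 5.2.2.1). SAP 7.8.2 derives a worst value and worst grade for every parameter. If the direction of concern decides which value is worst, the worst phosphate is the lowest one, and a patient whose phosphate rises after an infusion shows nothing of concern in that table. The protocol defines tumour lysis for this trial as clinical tumour lysis (Protocol 4.1.4.1.3), so the laboratory tables are a natural place for a reader to look for an earlier biochemical signal.

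For uric acid the issue is different. Two sections give incompatible statements about whether a grade exists. Two programmers working correctly from different sections could produce different grade-change tables for a prioritised parameter.

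**Working it through.** No sample size, error rate or event count is involved. The check follows each marker through SAP 5.4.5.1, 5.4.5.2 and 7.8.2.

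**Step 1. Compare the protocol's list with the SAP directions.**

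| Derangement named in Protocol 5.2.3.2 | Direction in SAP 5.4.5.1 | Covered there? | Among the four markers of 5.4.5.2? |
|---|---|---|---|
| High uric acid | + | yes | yes |
| High potassium | + and - | yes | yes |
| High phosphate | - | **no** | yes |
| Low calcium | + and - | yes | no |
| Uraemia (urea) | + | yes | no |

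One of the five named derangements, high phosphate, lacks its tumour-lysis direction in the general list. Creatinine, the fourth marker in 5.4.5.2, also has its direction (+).

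**Step 2. Trace a phosphate rise.** The values are assumed for illustration: 1.00 mmol/L before infusion and 1.50 mmol/L after.

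- Under 5.4.5.1, the value is not low, so it is not a direction of concern.
- Under Table 5.4.5.2:1, 1.50 ≥ 1.45, and the rise is (1.50 − 1.00)/1.00 = 50% ≥ 25%. Phosphate is abnormal.
- If phosphate alone is abnormal, the count is 1 of 4, below the required 2. The patient is not flagged.
- If phosphate is high and calcium is low, the count is still 1 of 4, because calcium is not one of the four. The calcium fall is a direction of concern in 5.4.5.1, but the phosphate rise is not.
- If phosphate and uric acid both qualify within 24 hours, the count is 2 of 4 and the patient is flagged. For example, with an assumed uric acid of 300 then 600 µmol/L: 600 ≥ 476, and the rise is (600 − 300)/300 = 100% ≥ 25%.

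The gap is thus a phosphate rise not accompanied, within 24 hours, by abnormal uric acid, potassium or creatinine.

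**Step 3. Trace uric acid.**

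- Direction: it is already (+), judged against the reference range. A raised value is a concern under 5.4.5.1 whether or not a grade exists.
- Grade, following 5.4.5.1: no grade is defined. Combined with the -9 rule of 7.8.2, the value would be analysed as grade 0. The SAP does not say this of uric acid; it follows only from joining the two rules.
- Grade, following the uric acid rule in 7.8.2: a value whose grade is ambiguous is listed as -1 and analysed as Grade 1. An unambiguous value takes its own CTCAE grade.
- For an ambiguous value after a baseline of grade 0, the change is 0 − 0 = 0 on the first reading and 1 − 0 = 1 on the second.

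**The case against.** The strongest reply is that the SAP has a dedicated tumour-lysis analysis, which does look at high phosphate, infusion by infusion, and 7.8.1.6 repeats the commitment. Requiring two markers is that analysis's case definition, and nothing in the documents shows the definition to be wrong. Tumour lysis is investigated mainly through adverse events, and clinically relevant laboratory changes are recorded as adverse events (Protocol 5.2.2.1). SAP 7.8.2 also promises summaries of clinically relevant abnormalities as defined in Section 9.2, which is not in the available text and may cover high phosphate. Protocol 7.3.3 promises that abnormalities of potential clinical relevance will be reported.

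Most of this stands and limits the severity. It does not remove the mismatch. The two-marker rule serves a different purpose from the general tables, and the general tables point the wrong way for phosphate. Other displays in 7.8.2 help only in part. Change from baseline to end of treatment can miss a short-lived rise after an infusion, and phosphate is not among the parameters listed for time-course plots. A maximum in the summary statistics shows an extreme value but not how many patients had a rise.

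On uric acid, a programmer could reasonably follow the 7.8.2 rule because it names the parameter. That is a fair prediction, but the statement in 5.4.5.1 names it too.

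Two stronger readings are tempting. A reader might infer that the SAP conceals the tumour-lysis direction of both markers. It does not: uric acid has the plus sign, and high phosphate is examined in 5.4.5.2. A reader might also infer that every raised uric acid will be analysed as grade 0 under one section and Grade 1 under the other. That goes too far: grade 0 is an inference from two rules, and the Grade 1 rule applies only where the grade is ambiguous.

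**Conclusion.** The point holds as a minor one, in two parts.

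First, the low-only direction for phosphate in SAP 5.4.5.1 conflicts with Protocol 5.2.3.2 and with the SAP's own Table 5.4.5.2:1. An isolated phosphate rise is not marked as a concern under 5.4.5.1 or 5.4.5.2. The effect on the worst-value table assumes that the sign determines which value counts as worst. That is the natural reading, but the SAP refers the details to an internal guideline that is not supplied. Whether Section 9.2 covers high phosphate could not be checked.

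Second, 5.4.5.1 and 7.8.2 contradict each other on whether uric acid has a CTCAE grade, and its grade-change results depend on which is followed. The documents show the disagreement but do not settle which statement is correct, because CTCAE 4.0 is not supplied.

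Neither part affects the MTD determination or the adverse-event route by which tumour lysis is mainly investigated.

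**What to change.** 1. In SAP 5.4.5.1, change inorganic phosphate to (+ and -), with high values judged against the reference range where no CTCAE grade applies. This costs about one extra table row and needs no new data.

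2. Reconcile 5.4.5.1 and 7.8.2 so that one grading rule applies to uric acid. Because 7.8.2 sets out a specific rule for this parameter, the likely edit is to remove URIC from the list of ungraded parameters, once CTCAE 4.0 has been checked. If that check shows no grade, remove uric acid from the -1 rule instead. Either way it is an edit of a line or two, and it should be made before the grade-change tables are programmed.

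3. While editing, confirm that Section 9.2 treats high phosphate in line with the revised 5.4.5.1.

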## **5.2.3 Assessment of safety laboratory parameters**

### **5.2.3.1 General safety laboratory parameters**

Blood samples and urine have to be collected at the time points specified in the [flowchart](#). Safety laboratory examinations will include haematology, biochemistry, coagulation and qualitative urine analysis.

Haematology	Haemoglobin, red blood cell count (RBC), white blood cell count (WBC) with differential, platelets (PLT)
	Reticulocytes have to be measured only at visit of the first and last administration of each treatment course, at the EOT visit and during follow-up.
Biochemistry	Glucose, sodium, potassium, calcium, inorganic phosphate, creatinine, aspartate amino transferase (AST), alanine amino transferase (ALT), alkaline phosphatase (AP), lactate dehydrogenase (LDH), total bilirubin (if elevated provide direct bilirubin), urea, total protein, albumin, uric acid
	Serum immunoglobulin levels (IgG, IgM, IgA), direct antiglobulin test have to be measured only at visit of first and last administration of each treatment course, at the EOT visit and during follow-up.
Coagulation	Activated partial thromboplastin time (aPTT), prothrombin time (PT)/international normalised ratio (INR)

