6.6 HANDLING OF MISSING DATA AND OUTLIERS

If not stated otherwise, missing data will not be imputed and remain missing. Potential outliers will be reported and analysed as observed.

Missing or incomplete AE dates are imputed according to BI standards (see [\(5\)](#)).

Missing data and outliers are handled according to 001-MCS-36-472 [\(2\)](#).

If the day of birth is missing, then the imputed days will be the 15th. If start of new NHL therapy date is incomplete (only month given), then the start date will be imputed with the 1st of month unless the first day leads to a date before the stop date of study medication, then the study medication stop date +1 will be imputed. If more than only the day is missing, dates will not be imputed.

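### Calcium drawn between safety panels to screen for tumour lysis gets no hypocalcaemia grade, because the SAP needs albumin from the same sample and the lysis panel has none

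*SAP*

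**What the plan says.** SAP 5.4.5.1 sets the basis for grading: "The grading of hypocalcemia is based on corrected calcium as calcium can be falsely low if hypoalbuminemia is present". It then limits when the corrected value exists: "Corrected calcium can be only derived at a certain time point in case both laboratory values, total calcium and albumin, have been reported". The sentence goes on to require that both "have been reported for the patient in the same laboratory sample".

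Protocol 5.2.3.2 gives the biochemistry of the tumour-lysis screen as "uric acid, potassium, calcium, inorganic phosphate, lactate dehydrogenase (LDH), creatinine, urea". Albumin is not listed. These samples are taken "every 4-8 hours between the time points at which a complete safety laboratory has to be performed", so they are additional to the safety panels. Albumin belongs to the general safety panel in protocol 5.2.3.1, whose biochemistry list ends with "urea, total protein, albumin, uric acid".

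No rule covers a calcium value without albumin. SAP 6.6 says that, unless stated otherwise, "missing data will not be imputed and remain missing". Protocol 7.4 allows screening values to stand in for missing baseline laboratory values and rules out any other imputation.

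SAP 7.8.2 takes the worst value and highest CTCAE grade for each laboratory parameter over all courses. It also tabulates changes in grade from baseline to worst, baseline to last, and worst to last. Total calcium and corrected calcium are both prioritized parameters, shown in Section 15 of the trial report.

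**The concern.** Protocol 5.2.3.2 names hypocalcaemia among the derangements of tumour lysis and orders frequent calcium measurement in the hours when lysis is most likely. The SAP's grading rule excludes those measurements, because the albumin it requires is not part of the panel. A fall in calcium that appears and recovers between two safety panels would not reach the hypocalcaemia grade tables.

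The error has one direction. The worst grade is a maximum over the graded samples, so leaving samples out can lower it and cannot raise it. The separate laboratory screen in SAP 5.4.5.2 does not fill the gap, because "laboratory signs of cell destruction will be investigated based on the laboratory values uric acid, potassium, inorganic phosphate and creatinine", and calcium is not among those four.

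At stake is the descriptive picture of early hypocalcaemia by dose cohort, in a trial where tumour lysis is a protocol-specified significant adverse event.

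**Working it through.** The plan states no figure of its own here, so the check compares the two panels and counts samples.

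**Panels side by side**
- General safety panel (protocol 5.2.3.1): calcium yes, albumin yes. Corrected calcium can be derived.
- Tumour-lysis panel (protocol 5.2.3.2): calcium yes, albumin no. Corrected calcium cannot be derived under SAP 5.4.5.1.

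**Inputs for the count**
- Interval: 4 to 8 hours (protocol 5.2.3.2).
- Windows: 48 h from the start of the first infusion in course 1 (72 h from the start of the low dose if split), then 24 h for the second infusion of course 1 and 24 h for the first infusion of course 2 (same section). Later infusions also have lysis monitoring, but without a fixed window, and are not counted.
- Safety panels: the Course 1 flowchart marks them on days 1, 2 and 3, and the split-dose flowchart (Appendix 10.7) on days 1 to 4.
- Assumption: one complete safety panel falls at each 24 h mark after the start of infusion and takes the place of a lysis sample there. The documents give days for the later panels, not clock times.

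**Formula:** samples without a grade = window ÷ interval − window ÷ 24.

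| Window | Every 8 h | Every 4 h |
|---|---|---|
| First infusion, 48 h | 6 − 2 = 4 | 12 − 2 = 10 |
| First infusion split, 72 h | 9 − 3 = 6 | 18 − 3 = 15 |
| Each 24 h window | 3 − 1 = 2 | 6 − 1 = 5 |

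- Share without a grade, first infusion: 4/6 = 67% to 10/12 = 83%. The split dose gives the same shares (6/9 and 15/18).
- All three windows, standard schedule: 4 + 2 + 2 = 8 to 10 + 5 + 5 = 20 without a grade, against 2 + 1 + 1 = 4 that can be graded.
- All three windows, split dose: 6 + 2 + 2 = 10 to 15 + 5 + 5 = 25, against 3 + 1 + 1 = 5.

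**Size of the correction left undetermined.** The SAP formula is corrected calcium = total calcium − 0.8 × (albumin − 4), in mg/dL and g/dL. For illustrative albumin values, the correction is −0.8 × (3.0 − 4) = +0.8 mg/dL at 3.0 g/dL and −0.8 × (2.5 − 4) = +1.2 mg/dL at 2.5 g/dL. Total calcium alone is therefore not a safe substitute for the corrected grade.

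**Can the gap be filled from data already collected?** With panels at 0, 24 and 48 h, no unpaired sample is more than 24 ÷ 2 = 12 h from an albumin value. A 24-hour pairing limit would cover the window with room for irregular timing.

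**The case against.** The case on the other side has real weight.

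- **The samples are not lost.** SAP 5.4.5.1 lists total calcium as a parameter in its own right, with low values a direction of concern. It is prioritized, and SAP 7.8.2 summarises its worst value and change from baseline. A reader might infer that no planned analysis uses the lysis-panel calcium. The documents do not support that. The SAP also refers to clinically relevant abnormalities defined in its Section 9.2, which is not in the public text, so whether calcium is used there cannot be judged.
- **Calcium in the window is not wholly ungraded.** Safety-panel samples there carry albumin and are graded, and any site that reports albumin with a lysis sample makes that sample gradable.
- **Tumour lysis is captured elsewhere.** SAP 5.4.5.2 investigates it mainly through adverse event reporting, and protocol 4.1.4.1.3 defines its presence by clinical criteria. Clinically relevant laboratory changes must be reported as adverse events. Protocol 5.2.1.1 bases DLTs on adverse events, so an inference that the MTD is at risk would be wrong.
- **Omitting calcium from the four markers looks deliberate.** The SAP history table records that this analysis was revised after a working-group decision. The marker set is not criticised here.
- **A repair has costs.** Borrowing albumin from another sample is arguably imputation under protocol 7.4. Hydration, which the protocol calls for, might lower albumin between draws. Grading uncorrected calcium would bring back the falsely low values that the SAP set out to avoid.

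These points narrow the reach of the finding and shape the remedy. They do not remove the gap: the SAP makes corrected calcium the basis for grading hypocalcaemia, and most lysis-window calcium values cannot be graded on it.

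**Conclusion.** The gap is real and limited. Samples taken between safety panels for tumour-lysis screening get no CTCAE hypocalcaemia grade unless albumin is reported voluntarily. The estimate is about 67-83% of samples in each window, and it rests on safety panels falling at the 24 h marks. The worst hypocalcaemia grade and the shifts built on it can miss a low point and so can only understate its depth.

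The count concerns samples. It does not show that any patient's worst grade would change, and the documents hold no data from which to tell. A reader might also infer that an unpaired low calcium would be counted as normal, because SAP 7.8.2 treats the code for no defined CTCAE grade as grade 0 in change-from-baseline analyses. The SAP does not say whether that code applies to unpaired calcium, so this stays open.

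The primary endpoint is not affected. The plan should be corrected because the omission falls in the hours the screen was designed to cover, and the data to fill it are already collected.

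**What to change.** In SAP 5.4.5.1:

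1. Keep the same-sample derivation as the main one.
2. Add a supplementary derivation that corrects unpaired calcium with the patient's nearest albumin within 24 hours, and flag each such value.
3. Report the worst-grade and shift tables for hypocalcaemia (SAP 7.8.2) with and without the flagged values.
4. Where no albumin lies within 24 hours, list low total calcium against its reference range. Do not mix uncorrected grades into the main tables.
5. State that the pairing is an exception to the no-imputation rule of protocol 7.4.

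The cost is SAP wording, a short derivation and one additional version of the affected tables. No new samples are needed. The downside is some imprecision when albumin changes within 24 hours, for example with hydration. If albumin has fallen since the paired value was drawn, calcium is under-corrected and hypocalcaemia overstated. The flag and the display with and without the paired values let the reader see how much depends on this.
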